1. INTRODUCTION

1.1 General Introduction

Dental implants have become an important and popular treatment option to replace absent or lost teeth. It is expected that implant prevalence could reach as high as 23% of US adult population by 2026 based on current NHANES data trends (Elani et al. 2018). The survival rate of dental implants is as high as 96.8% for 5 years and 92.8% for 10 years (Jung et al. 2007). Over time, the reported survival rates for all types of implant restorations have continued to increase, however, the incidences of esthetic, biologic, and technical complications are still high (Pjetursson et al. 2014). If untreated, complications associated with implant dentistry may result in progressive inflammation, bone loss, and ultimately, implant failure. Peri-implant mucositis is defined as inflammation in the peri-implant mucosa without peri-implant bone loss (Heitz-Mayfeild & Salvi, 2018). Clinical signs of inflammation of the peri-implant mucosa include bleeding on probing, erythema, swelling, and suppuration (Heitz-Mayfeild & Salvi, 2018). Peri-implantitis is defined as a pathological condition around implant tissues with inflammation and progressive loss of supporting bone around the implant (Schwarz et al. 2018). Clinically, peri-implantitis includes the presence of inflammation, radiographic bone loss, and increasing probing depth (Renvert et al. 2018). The etiology of peri-implant mucositis and peri-implantitis is through the development and accumulation of a bacteria biofilm around the implant. Peri-implant disease etiology is similar to the etiology of gingivitis and periodontitis. Disease is caused by the host response to a bacterial biofilm with a shift in bacterial species and type as the disease progresses. Biofilm-induced peri-implant mucositis is reversible by the removal of plaque from around the implant (Salvi et al. 2011). It is important to treat peri-mucositis professionally through mechanical removal of bacteria biofilm, preventing disease progression to peri-implantitis and prevent implant loss (Schwarz et al, 2015). The gold standard of care in the treatment of inflammation of implants is the mechanical removal of plaque with the use of curettes and ultrasonics. Conventional mechanical debridement of the implant surface is limited by the contaminated microstructure of the implant surface. Bacteria might be protected by residing in micro-irregularities of the titanium implant surface. Therefore, antimicrobial adjuncts have been advocated to increase the range of effective treatment in reducing inflammation around implants over the usual standard of mechanical debridement (Figuero et al. 2014). Options of adjuncts in the treatment of peri-implant inflammation include systemic antibiotics, local antibiotics, and antiseptics. Laser therapy such as antimicrobial photodynamic therapy (aPDT) can be used as an adjunct in the treatment of peri-implant mucositis and peri-implantitis. Antimicrobial photodynamic therapy uses low level laser light and aims to destroy pathogens around the implant and can also act as a photobiomodulator reducing inflammation and stimulating cellular proliferation (Mizutani et al. 2016). The advantages of aPDT are its wide antimicrobial activity, can be applied multiple times without creating antibiotic resistance, and easier topical delivery reaching the micro-irregularities of the implant surface.

1.2. Rationale and justification for the Study

a. *Rationale for the Study Purpose*

So far, there is limited evidence supporting the clinical impact of aPDT in the treatment of peri-implant diseases. The main goal of treating inflammation around implants is to reduce the bacterial biofilm. Mechanical debridement can disrupt this biofilm but cannot eliminate bacteria within the micro irregularities of the titanium implant surface. It is important to assess the use of aPDT as an adjunct to

mechanical debridement. Adjunctive use of aPDT may overcome the disadvantages of systemic and local antibiotic adjuncts and to overcome limitations of mechanical debridement of implant surfaces. A limited number of articles have evaluated the efficacy of aPDT with the use of laser (Diode Laser) and photosensitizing dye (Methylene blue). Bassetti *et al.* (2013) compared the use of locally delivered antibiotics and antimicrobial photodynamic therapy in 40 patients who had initial peri-implantitis. All implants were treated with mechanical debridement then were randomly treated with either local antibiotics or aPDT. Both groups had a decrease in BOP, PD, bacteria, and proinflammatory cytokines. This study showed that aPDT can be just as effective as locally applied antibiotics without challenges and risks of antibiotic use. Kerimin *et al.* (2016) in a randomized split mouth clinical trial showed that the aPDT test groups had statistically greater reduction in gingival inflammation, BOP, and probing depth than those implants treated with mechanical debridement alone. Few clinical trials have thoroughly evaluated aPDT as an adjunct to mechanical debridement of implants with peri-mucositis and peri-implantitis (Lin *et al.* 2017).

b. Rationale for Materials Selected

Mechanical debridement with curettes of implant surfaces have been shown to reduce and reverse peri-implant inflammation. Antimicrobial photodynamic therapy, used with a diode laser, works through an interaction between the photosensitizer (methylene blue or toluidine blue), red light (625–740 nm), and oxygen. The methylene blue dye is taken up by the bacteria and the visible red light excites the dye. The excited dye transfers energy to tissue oxygen forming a singlet oxygen molecule. Singlet oxygen is highly reactive and will affect the bacterial cell by damaging the cell membrane and cell wall. The bactericidal effect is through DNA damage and more importantly damage to the cytoplasmic membrane (Takasaki *et al.* 2009). The photosensitizer, such as methylene blue, undergoes a strong cationic charge, which can bind to the outermost membrane of gram-negative bacteria and can penetrate bacterial cells. This creates selectivity of the dye to affect bacterial cells rather than human tissue cells (Takasaki *et al.* 2009). Also, the singlet oxygen molecule has a short lifetime and limited migration, so the reaction and cellular damage is contained within a limited space (Takasaki *et al.* 2009).

c. Rationale for Study Population

The study will recruit subjects who have an implant diagnosed with either peri-mucositis or peri-implantitis based on the 2017 World Workshop periodontal classification (Renvert *et al.* 2018). The gold standard to treatment inflammation around implants is mechanical debridement. All patients recruited are in need of traditional mechanical debridement.

d. Rationale for Study Design

It is a randomized double blinded clinical control study. The randomized controlled trial (RCT) is usually considered the gold standard for a clinical trial and it is able to provide the highest level of evidence within all the study designs. Two treatments (test and control) are randomly assigned to a single implant for each patient. Both the examiners and patient will be blinded to which treatment was completed. The investigator completing the treatment will not be blinded. This design removes examiner and patient bias and placebo effects.

2. HYPOTHESIS AND OBJECTIVES

2.1 Hypothesis

Null hypothesis: Antibiotic photodynamic therapy (aPDT) has no statistically significant advantage over traditional non-surgical mechanical debridement in improving clinical outcomes (# bleeding sites (BOP), probing depth reduction (PPD), or reduction in levels of pathologic microbes) in the treatment of implants with peri-implant inflammatory disease.

2.2 Primary Outcome Measures

This study aims to compare clinical outcomes (change in BOP and PPD) after mechanical debridement of implant surfaces at sites exhibiting plaque induced inflammation with or without adjunctive aPDT. Bleeding on probing and periodontal probing depths will be assessed clinically through a periodontal probing exam at baseline, week 6, and week 12 follow up. Probing depth reduction endpoint value of 1mm (Bassetti et al. 2014, Morrison et al. 1980). Bleeding on probing endpoint value of 50-60% reduction of sites with BOP (Bassetti et al. 2014). Demographic and implant related variables will be analysed using multivariate analysis for correlation with peri-implant mucositis and peri-implantitis.

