3.3 Inclusion Criteria

Sixty-four subjects will be recruited amongst patients attending the Clinic for Graduate Periodontics, Graduate Prosthodontics, or the UTDentists, who have at least one implant with peri-implant inflammation that requires non-surgical treatment. Peri-implant diseases included are peri-implant mucositis and peri-implantitis. All subjects will be ≥ 18 -year-old and systemically healthy or with controlled common systemic conditions, such as hypertension, that will not affect wound healing. Criteria for diagnosis of peri-implant mucositis or peri-implantitis:

1. Red, swollen gingival tissues surrounding the implant
2. Presence of bleeding and/or suppuration on gentle probing around the implant
3. Increased probing depth compared to probing depth after restoration of the implant (greater than 2mm increase in probing depth)
4. May or may not have progressive bone loss in relation to radiographic bone levels assessed either 1 year following restoration of the implant OR ≥ 3 mm of radiographic bone loss from the implant platform

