5. STUDY DESIGN

5.1 Summary of Study Design

This is randomized double blinded clinical control study designed to assess improved clinical and microbiological outcomes with the use of laser antimicrobial photodynamic therapy (aPDT) as an adjunct to the gold standard of mechanical debridement in the treatment of peri-implant diseases. Seventy-four patients will be recruited. Clinical measurements including bleeding on probing, pocket depth, plaque, and clinical attachment will be measured at baseline, 6 weeks, and 12 weeks after therapy. The 2017 World Shop classification will be used to diagnosis implants as peri-implant mucositis or peri-implantitis (as stated above in section 3.3). Only diseased implants will be included and only one implant per patient will be studied. The hypothesis is that inflamed implant sites treated with mechanical debridement and adjunctive aPDT will have greater reduction in bleeding and pocket depth reduction than those sites treated with mechanical debridement alone. The potential for greater healing and greater antibacterial activity on the implant surface will benefit patients who have peri-implant diseases. The results can be applied in the managing and in the armamentarium for treatment of both peri-implantitis and peri-implant mucositis.

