reviewed with all patients including techniques to clean around implants. Mechanical debridement of implant surfaces will be completed with titanium scalers and ultrasonics removing supragingival and subgingival plaque. Antimicrobial photodynamic therapy will be done at implant sites by applying a photosensitizing dye methylene blue (0.1 mg/ml) with a disposable syringe from the bottom of pocket in a coronal direction. The methylene blue dye will be diluted from 1.0% to 0.1% before use. The dye will be applied topically confined to the epithelialized space surrounding the implant fixture and will not be internalized. After 5 minutes in situ, the surrounding gingival tissues will be irradiated at six sites around the implant using a diode laser with a wavelength of 660nm, providing an energy density of 10 J/site, 100mW power, time equal to 100 seconds. After irradiation, the site will be thoroughly rinsed with saline. Only pockets \geq 4mm will be treated with the diode laser as this is the threshold pocket for diagnosing peri-implant inflammation per the 2017 World Work Workshop (Heitz-Mayfield & Salvi, 2018).

Clinical Measurements

Implant sites will be evaluated at baseline, six weeks, and twelve weeks after treatment (2 follow-up visits in total). Improvement in sites resulting from a reduction in inflammation will be analyzed based on pocket depth, clinical attachment loss, bleeding on probing, and the presence of plaque. For clinical measurements, six sites around the implant will be measured: mesial buccal, mid buccal, distal buccal, mesial lingual, mid lingual, and distal lingual. Bleeding on probing will be evaluated by gently sweeping the periodontal probe just within the gingival sulcus of the implant and the presence or absence of bleeding will be recorded. The presence or absence of plaque will then be evaluated at six sites around the implant surface. Plaque sampling will be performed prior to the remaining clinical measurements at the baseline/treatment appointment and 12 weeks after treatment utilizing a titanium curette within the gingival sulcus of the inflamed site. Periodontal pocket depth is measured from the free gingival margin to the base of the pocket, with a UNC periodontal probe with 1mm measurement units. Clinical attachment loss is measured by subtracting the pocket depth from distance of the free gingival margin to the implant platform.

Microbiologic collection and analysis

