11.2 Statistical and Analytical Plans

a. General Consideration

We will present means and standard deviations for completeness of the report. The statistical significance level to test the primary endpoint was set at $p<0.05$.

b. Safety Analyses

Safety will be evaluated by tabulations of adverse events and will be presented with descriptive statistics at baseline and follow-up visits each month.

Adverse events will be classified as severe complications and summarized for baseline and follow-up visits.

All information pertaining to adverse events noted during the study will be listed by subject, detailing verbatim given by the investigator, preferred term, date of onset, date of resolution, severity, and relationship to procedure. The onset of adverse events will also be shown relative (in number of days) to the day of performing the surgery.

c. Statistical Analysis Plan

We will analyze these data sets using generalized linear mixed effects models with the appropriate error structure (e.g., binomial, poisson) and specifying treatment (control mechanical debridement vs mechanical debridement + aPDT) as a fixed factor and repeated measures of individuals over 0, 6, and 12 weeks as a random factor. Demographic data collected from patients will be included in analysis and will be adjusted for any confounders. All quantitative analyses will be performed in R Statistical Software (R Core Team 2017).

For microbiologic analysis, microbial DNA will be purified using the QIAmp DNA Mini Kit (Qiagen, Hilden, Germany) or Qiagen DNA MiniAmp kit (Qiagen, Valencia, CA, USA), according to the manufacturer's protocol. 16S rRNA gene V4 amplification and sequencing will be completed. 16S rRNA gene data analysis will also be completed for the plaque samples.

For immunologic analysis, the PerioPaper strips will be analyzed using multiplexed fluorescent bead-based immunoassay. Assessments will be made in triplicate, and for the statistical analysis, median of the replicates will be used.

12. Ethical Consideration

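### The primary BOP endpoint value is a 50-60% range with no stated role, so any responder result or claim that it was met could use either end after the data are seen

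*Combined protocol and SAP*

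**What the plan says.** Section 2.2 says the study will "compare clinical outcomes (change in BOP and PPD") at baseline, week 6 and week 12. It then attaches a value to each measure. Probing depth gets a single figure, "Probing depth reduction endpoint value of 1mm", while bleeding gets a range, "Bleeding on probing endpoint value of 50-60% reduction of sites with BOP". Both carry literature citations. The null hypothesis in 2.1 treats bleeding as a count of sites.

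The measurement scale is set elsewhere. Section 5.1 states that "only one implant per patient will be studied"; section 6.3 states that "six sites around the implant will be measured" and that at each "the presence or absence of bleeding will be recorded". So each patient contributes a count from 0 to 6 at each visit.

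Section 11.2c plans "generalized linear mixed effects models with the appropriate error structure (e.g., binomial, poisson"), with treatment as the fixed factor and repeated measures at weeks 0, 6 and 12. It contains no responder variable and no threshold. No other section narrows the 50-60% range.

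**The concern.** A figure presented as an endpoint value under primary outcomes invites the report to say whether it was reached. If it serves that purpose, it has to be one number with an inequality, a visit and a level. Here all four are missing. Read per patient, the two ends of the range can give two responder rates from the same data. Read per arm, any observed mean reduction between 50% and 60% reaches one end and misses the other.

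Sections 1.2d, 6.1 and 8.3 describe blinding of patients and examiners. They do not say that whoever would pick the cut-off is blinded to results. At stake is the credibility of a secondary reading of the primary outcome: a responder comparison, or a statement that a clinically meaningful reduction was achieved.

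**Working it through.** The plan derives no figure from the 50-60% value, so there is none of its own to reproduce.

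**Step 1: which patients are affected.** Inputs from the plan: one implant, six sites, each present or absent. Let k be the number of bleeding sites at baseline and j the number that resolve. The reduction is j/k.

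| k | attainable reductions (%) | differs between ≥50% and ≥60% |
|---|---|---|
| 1 | 0, 100 | never |
| 2 | 0, 50, 100 | j = 1 |
| 3 | 0, 33.3, 66.7, 100 | never |
| 4 | 0, 25, 50, 75, 100 | j = 2 |
| 5 | 0, 20, 40, 60, 80, 100 | never |
| 6 | 0, 16.7, 33.3, 50, 66.7, 83.3, 100 | j = 3 |

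No attainable value lies strictly between 50% and 60%, so every at-least cut-off above 50% and up to 60% gives the same classification. The real choice is whether exact halving counts. With strict greater-than cut-offs, only 3 of 5 is classified differently, so the missing inequality matters as well.

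**Step 2: what share of patients that is.** The documents give neither baseline counts nor resolution rates, so these are assumptions. If each bleeding site resolves independently with probability q, the share affected at even k is C(k, k/2) q^(k/2) (1−q)^(k/2).

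- At q = 0.5: k = 2 gives 0.500, k = 4 gives 0.375, k = 6 gives 0.3125. For k = 6 the responder rates are 0.656 (≥50%) and 0.344 (≥60%).
- Baselines spread evenly over 2 to 6, q = 0.5: (0.500 + 0.375 + 0.3125)/5 = 0.2375, that is 61.9% against 38.1% responders. At q = 0.4 the rates are 45.8% against 23.8%; at q = 0.6, 76.2% against 54.2%; a gap of 22 points in both.
- Baselines spread evenly over 1 to 6, q = 0.5: 1.1875/6 = 0.198.
- Baseline count binomial over six sites with at least one bleeding, bleeding probability 0.67 per site, q = 0.5, independent sites: 59.6% against 40.4%, a gap of 19.2 points; 0.192 × 64 = 12.3 patients.
- Same type of model with baseline probability 0.5 to 0.8, q from 0.4 to 0.7, and within-patient correlation of resolution 0 to 0.4 (beta-binomial): from 6.5% (0.8, 0.7, 0.4) to 21.3% (0.5, 0.5, 0).

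The range over all these assumptions is about 6.5% to 24%, or 0.065 × 64 = 4 to 0.2375 × 64 = 15 of the 64 planned evaluable patients. If every baseline count were odd, it would be zero.

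**Step 3: what choosing the cut-off would do to a responder test.** This was simulated with no treatment effect: 32 per arm, 20,000 runs, an uncorrected two-proportion z-test at two-sided 0.05, baseline probability 0.67 or 0.8, q of 0.5 or 0.6, correlation 0 or 0.2.

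- One fixed cut-off: type I error 4.9% to 6.0%.
- Significant at either cut-off: 8.6% to 9.7%.

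The simulation standard error near 9% is √(0.09 × 0.91/20,000) = 0.2 points.

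**Step 4: the planned test.** The model in 11.2c does not contain the threshold. Its p-value is the same whichever end of the range is read.

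**Step 5: a related gap.** An entry criterion in 3.3 is "Presence of bleeding and/or suppuration on gentle probing around the implant", so a patient could enter on suppuration with no bleeding site. A percentage reduction would then be undefined; a count would not.

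**The case against.** The strongest reply is that no responder endpoint exists in these documents. The primary outcome is change, the null hypothesis speaks of a count, 5.1 hypothesises a greater reduction, and 11.2c models repeated measurements. Both values in 2.2 come with citations, which fits an expected or clinically relevant magnitude, and a range is normal for that. Changing the cut-off also moves both arms, so a shift in the overall responder rate is not itself a bias in the comparison.

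Most of this stands. A reader might infer that the range lets the investigators decide whether the trial succeeds. The documents do not support that: they define no success rule based on the value, and the planned test does not use it. A reader might also infer that many patients change category. That is not established either: only exact halving from an even baseline is affected, and the share rests on distributions the documents do not give.

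The objection does not supply a role for the value. The benchmark reading is plausible but unstated, and the binomial option in 11.2c would fit a responder variable as well as site counts. The point about both arms moving is fair for the responder rates in step 2; step 3 addresses the between-arm test directly, though only on the condition that such a test is run.

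**Conclusion.** The point holds as an unresolved specification in a primary outcome. It is not a flaw in the planned test. The BOP endpoint value is a range without inequality, visit, level or role, and nothing in the plan prevents a responder result, or a claim that the value was met, from being stated at whichever end suits. The algebra of who is affected is exact: with at-least cut-offs, halving from 2, 4 or 6 sites and nothing else. The share of about 6.5% to 24% depends on assumed baseline and resolution patterns. The type I error of about 9% depends on those too, and on a responder test being added and the better cut-off kept. The correction costs little, so it should be made before analysis.

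**What to change.** In 2.2 and 11.2c, state that the primary BOP analysis is the treatment contrast at week 12 in the number of bleeding sites out of six, from a binomial model that allows for within-patient correlation and adjusts for the baseline count. Week 6 can stay in the repeated-measures model as a post-baseline visit. This matches the count in 2.1 and uses an error structure 11.2c already offers. It also says which visit carries the comparison; at present treatment is the only fixed factor named, over a series that includes baseline.

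Remove 50-60% as a possible success criterion in one of two ways:

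- label it a descriptive benchmark that decides nothing; or
- report one supportive responder rate with a single pre-specified cut-off, for example at least 50% reduction at week 12 among patients with at least one bleeding site at baseline. The documents do not favour 50% over 60%; what matters is that one value and its inequality are fixed in advance.

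The cost is about two sentences, and week 6 becomes supportive. No visit, measurement or sample-size change is needed.

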2.3 Secondary Outcome Measures

In addition to the clinical outcomes, plaque samples and peri-implant sulcular fluid (PISF) will be taken to assess the microbiologic and immunologic profile before and after treatment with or without aPDT. Subgingival biofilm samples will be collected using sterile titanium implant scalers and will be assessed at baseline and week 12 follow up. PISF will be collected from the tested implant site after clinical examination. The levels of interleukin (IL)-1 α , IL-1 β , IL-6, IL-8, IL-10, IL-12, IL-7A, tumor necrosis factor (TNF)- α , C-reactive protein, osteoprotegerin, leptin, and adiponectin will be determined using multiplex proteomic immunoassays.

2.4 Potential Risks and Benefits:

a. End Point – Efficacy

All eligible patients needing non-surgical treatment of peri-implant disease will receive the appropriate treatment of mechanical debridement. The mechanical removal of plaque around the implants is the gold standard of care in the treatment of implant inflammation. The patients in the adjunctive aPDT group may have improved healing as observed through surrogate clinical measures of inflammation (BOP, PPD), greater microbiologic reduction, and levels of key biomarkers in PISF that resembles peri-implant tissue health (Recker 2015).

b. End Points – Safety

1) Study related risks:

Initial mild pain, swelling, and bleeding related to non-surgical implant surface mechanical debridement. Potential for antimicrobial methylene blue dye to reversibly stain gingiva around implant site. Collecting PISF will not result in any additional side effects. Patient will not be provided medications for study

related pain. If patient reports pain after treatment will recommend over the counter analgesics such as ibuprofen or acetaminophen.

2) Protection against risk:

All efforts will be made to minimize risks to all and every participant. Laser safety protocols will be followed including laser safety mechanisms, labels and signage, safety zone implementation, proper eye protection for patient and clinician.

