6.3 Study Visits and Procedures

a. Screening Visits and Procedures

Study protocol and consent forms will be approved by the Institutional Review Board at the University of Texas Health Science Center at Houston. The trial will be registered with ClinicalTrials.gov. The clinicians treating patients at UTSD will be told the information of this clinical trial. The potential subjects will be identified in the clinic of Department of Periodontics, Prosthodontics, or UTDentists for initial screening. The principal investigator will confirm the eligibility of these patients.

All patients will sign the consent forms and will be informed of the details of study procedures as well as potential complications. After informed consent is obtained, the non-surgical implant therapy will be scheduled as the first visit.

Patient's Demographic Data Collection

Upon enrollment into the study and patient's consent form signed, patient's demographic data from patient's electronic health record (EHR) in the UT School of Dentistry will be collected. This information will include, but not limited to, patient's de-identifiable chart number, age, gender, race, medical history, dental conditions, and all pertinent dental implant related data. Radiographic information regarding the implant(s) included in the study will also be collected prior to treatment.

b. Study Visits and Procedures

Patients will be randomly divided into 2 treatment groups. (A) Test group: patients will undergo traditional non-surgical mechanical debridement with adjunctive use of aPDT at implant(s). (B) Control group: patients will undergo traditional non-surgical mechanical debridement alone with “sham” aPDT with saline and non-light emitting laser at implant(s). Clinical measurements and PISF will be collected at the baseline appointment, and at follow up 12 weeks after treatment. For PISF collection, the volume of fluid collected will be measured using Periotron then stored in -80° C freezer. Plaque samples will be taken at baseline and at the 12-week appointment. Full mouth prophylaxis or periodontal maintenance will be completed with ultrasonics, hand instruments, and prophylaxis paste. Oral hygiene instructions will be

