Plaque samples will be taken from the deepest probing site of each implant before and 12 weeks after PDT. If more than one sites presented similar probing values, the most anterior site would be chosen for ease of obtaining an appropriate sample. The sample sites will first be isolated by cotton rolls and supragingival and marginal plaque will be removed before subgingival biofilm samples collected using sterile titanium implant scalers (Hu-Friedy). The collected samples will be immediately placed in separate sterile Eppendorf tubes containing 0.15 ml TE (10 mM Tris-HCl, 1 mM EDTA, pH 7.6). Samples will be stored at -80°C until further analysis. DNA will be purified using the QIAamp DNA Mini Kit (Qiagen, Hilden, Germany) or Qiagen DNA MiniAmp kit (Qiagen, Valencia, CA, USA), according to the manufacturer's protocol. 16S rRNA gene V4 amplification and sequencing will be completed. 16S rRNA gene data analysis will also be completed for the plaque samples.

PISF collection and analysis

PISF will be collected from the sulcus around the target dental implant using paper strips (PerioPaper, Oraflow). In patients with multiple implants, preference will be given to the implant included in the study. With proper isolation using cotton rolls in the buccal and lingual aspects of the study site, the area will be dried for 5 seconds with compressed air. The paper strip will be gently introduced into the

mucosal crevice around the dental implant for 30 seconds per site in four sites (mesial, distal, facial/buccal, lingual/palatal). The strips will then be removed from the crevice, and the volume of fluid collected in each strip measured using a micromoisture metering device (Peritron, Oraflow). After confirming the adequateness of the volume, the paper strips from each implant will be transferred into labeled tubes and stored at -80° C for later use. For analysis, the paper strips will be analyzed using multiplexed fluorescent bead-based immunoassay. Assessments will be made in triplicate, and for the statistical analysis, median of the replicates will be used.

c. Final Study Visit

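### PISF strips are scheduled after the clinical examination and 6.3b does not place them in the visit order, so they may follow probing that provokes bleeding and carry blood of unknown effect

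*Combined protocol and SAP*

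**What the plan says.** Section 2.3 lists PISF biomarkers as a secondary measure and fixes their place in one sentence: "PISF will be collected from the tested implant site after clinical examination". It does not say what that examination contains. Section 2.2 says that BOP and probing depth are "assessed clinically through a periodontal probing exam at baseline, week 6, and week 12 follow up".

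Section 6.3b gives the visits: "Clinical measurements and PISF will be collected at the baseline appointment, and at follow up 12 weeks after treatment". Under Clinical Measurements it describes an order for the other steps. First, "Bleeding on probing will be evaluated by gently sweeping the periodontal probe just within the gingival sulcus of the implant"; next, "The presence or absence of plaque will then be evaluated at six sites around the implant surface"; and "Plaque sampling will be performed prior to the remaining clinical measurements". Under the microbiology heading, "Plaque samples will be taken from the deepest probing site of each implant before and 12 weeks after PDT". PISF does not appear in this order.

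The strip technique in 6.3b consists of cotton-roll isolation, 5 seconds of compressed air, 30 seconds per site at four sites, and confirmation that the volume is adequate. Adequate is not defined. The text mentions neither a wait after probing nor a check for blood. Appendix 1, the data collection form, is listed but not reproduced.

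**The concern.** The strips enter the same sulcus that the BOP test sweeps with a probe. Section 3.3 makes bleeding and/or suppuration on gentle probing a diagnostic criterion, so bleeding after probing is to be expected in these implants. If strips are taken afterwards, the fluid read for volume and sent to the immunoassay may be part blood. Subgingival plaque sampling with a titanium curette is a second possible source of bleeding, and its order relative to the strips is also unstated.

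At stake is the quality of a secondary measure that 2.4a names as a possible benefit of aPDT. Two operators, or one operator at two visits, could also follow the present text and sample in different orders.

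**Working it through.** The plan gives no figure to reproduce on this point, so the check sets the sections side by side.

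1. **Order.** Section 2.3 puts PISF after the clinical examination, 2.2 describes the assessment as a probing exam, and 6.3b provokes BOP with a probe in the sulcus. Read together, strips follow probing. Section 6.3b orders BOP, plaque presence, plaque sample and remaining measurements, but never the strips, so it neither confirms nor corrects 2.3.

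2. **Safeguards.** Isolation and drying may reduce contamination. The only stated acceptance step concerns volume. No blood check is stated in the text; what the form asks is not known.

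3. **Direction.** Let f be the share of strip fluid that is blood, C the analyte concentration in PISF and B its concentration in blood. The measured concentration is (1 − f)C + fB, a shift of f(B − C). The sign depends on whether B is above or below C, and the documents give neither for any listed analyte. They also speak only of levels. If the amount per strip is analysed instead, added blood would not generally dilute the result and this rule need not hold. So no direction can be stated.

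4. **Before-after change.** If f falls as bleeding falls, the shift differs between baseline and week 12 even when C is constant. Section 2.2 sets a "Bleeding on probing endpoint value of 50-60% reduction of sites with BOP", so a fall in bleeding is what the plan looks for. Apparent biomarker change could then be partly a change in contamination.

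5. **Between arms.** Both arms follow the same procedure. With no true difference in C and the same f in each arm at week 12, the shift cancels. A spurious difference needs f, hence bleeding, to differ by arm. That is the effect which 5.1 hypothesises, so the condition is plausible but not established.

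6. **Size.** This would need f and B/C, and neither is in the documents. The 50-60% in 2.2 is an endpoint for reduction, not a pair of expected arm values. Any numeric range would restate invented inputs, so none is given.

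**The case against.** The strongest reply is that this is a minor gap in a secondary measure. The biomarkers are not among the outcomes named in the null hypothesis (2.1), both arms are sampled alike, examiners are blinded, and no section links blood on strips to any analyte. This stands as a limit on importance. It does not remove the point, because 2.3 states an order, and following it as written puts strips after provoked bleeding.

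A second reply is that the cure touches a primary outcome. PISF is taken at baseline and week 12 only, whereas BOP is measured at weeks 0, 6 and 12 and all three enter the mixed model in 11.2c. Strips before BOP would make the conditions at week 6 differ from those at the other visits. This also stands. The difference would be the same in both arms, but it must be disclosed and kept small.

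Third, the plaque sample is to come from the deepest probing site, yet is taken before the remaining measurements. If depths are probed at that visit to find the site, strips are no longer ahead of probing. This gap already exists in the protocol and has to be closed as part of the fix.

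Some stronger readings are not supported. A reader might infer that a blood-stained strip would pass the volume check; adequacy is undefined, so the documents do not show this. A reader might infer that blood is never recorded; the form in Appendix 1 could not be checked. A reader might take a correlation between biomarkers and BOP as proof of an artefact; both reflect inflammation, so it would not be.

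**Conclusion.** The point holds as a cheap improvement, with medium confidence. The stated order probably puts strips after probing, and 6.3b leaves their position open. The consequences are noise in PISF volume and biomarkers, possible distortion of before-after change, and bias between arms only if bleeding differs by arm at week 12. Size and direction are unknown, and the effect may be small.

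This rests on reading the clinical examination in 2.3 as including probing. If something narrower is meant, the text still needs to say so. It also rests on blood differing from PISF in analyte content, which the documents do not address.

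Two larger conclusions are tempting and should be resisted. The documents do not show that the biomarker comparison is biased, still less that it favours aPDT. Nor does the current order affect BOP or PPD.

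**What to change.** - **Section 2.3:** replace the words that put PISF after the examination with wording that places it before any probing or subgingival plaque sampling at that visit.
- **Section 6.3b:** state the same position for the strips at both baseline and week 12, with the existing order of the other steps following. Do not add marginal plaque clearance before BOP beyond what 6.3b already describes for the microbiology site.
- **Deepest site:** state how it is known before PPD is measured at that visit, for example from earlier recorded depths.
- **Blood:** record visible blood on each strip, if the form does not already do so. Keep all samples in the main analysis. Label any analysis of flagged strips exploratory, because week-12 blood arises after randomisation and is related to a primary outcome.

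**Cost:** no new visit or assay, at most one added form field, and an amendment with IRB approval under 12.2. Gentle strip insertion would precede BOP at weeks 0 and 12 but not week 6, and would precede the plaque sample, where it may slightly disturb the biofilm; both apply equally in the two arms. If enrolment has begun, samples may exist in two orders, so record the order used for each sample and keep it constant within a patient.
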